STATISTICS Primary Analysis Plan	We will compare levels of Tenofovir DiPhosphate (TFV-DP), the phosphorylated active tenofovir molecule in dried blood spots and rates of adverse events between trans men and trans women and a group of MSM historical controls from the iPrEx OLE study. We will compare log transformed TFV-DP levels using a linear mixed effects model with factors for group (trans men v. trans women v. MSM) and times (1, 2, 3 and 4 weeks after initiation) and their interaction with an unstructured covariance across visits and test for differences at between groups at each time point. If values appear to violate the normal distribution, we will obtain p-values and confidence intervals using the bootstrap. All p-values will be two-sided with p-value < 0.05 considered statistically significant. Adverse events will be compared using the Fisher exact test.
Rationale for Number of Participants	A sample size of 48 (24 trans women and 24 trans men) allows detection of a difference of 0.52 log difference (1.68 fold difference) in TFV-DP from dried blood spots with 81% power on a two-sided 0.05 level test at any time point between our trans participants and MSM historical controls. A difference of 0.70 log (2.0 fold difference) can be detected between either group (trans men or women), and MSM historical controls with 80% power on a two-sided 0.05 level test.

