## 2.2 Overview of Clinical Studies

There have been a large number of trials conducted with Truvada PrEP, including several demonstration projects. While there is no evidence to suggest that TDF/FTC interacts with commonly used feminizing or masculinizing hormone regimens, and evidence from studies of ARV interactions with hormonal contraceptives have been reassuring, no direct study of these interactions has been conducted to date.

Our team led the only trans-specific sub analysis to date of the iPrEx randomized controlled trial (RCT) data as well as the open label extension (OLE) study, which included periodic dried blood spot (DBS) drug level monitoring [2]. In iPrEx, gender identity data was not collected using current best practices (“two-step” method [5]), making the identification of transgender participants in this multinational, multicultural and multilingual trial difficult. As all iPrEx participants had been assigned male sex at birth, a transgender subgroup of 339/2499 participants (14% of overall sample) was constructed comprised of the 29 (1%) who identified as women, 296 (12%) who identified as “trans”, and 14 (1%) who reported use of feminizing hormones. None had undergone gender affirming genital surgery. Compared with MSM, transgender women more frequently reported transactional sex, receptive anal intercourse without a condom, or more than 5 partners in the past 3 months. Excluding those with a male identity who also used feminizing hormones, trans- and woman-identified participants were less likely to have TDF levels detected on random testing in the RCT (OR=0.39, 95% CI = 0.16 to 0.96, p=0.04). While there was no effectiveness of PrEP for transgender women on an intention-to-treat basis, none of the transgender participants who seroconverted had detectible drug levels at the time of HIV diagnosis. In comparison to MSM in the OLE, transgender participants had less time with protective drug concentrations (17% vs 35%, p<0.001) and were less likely to have concentrations indicating > 3 tablets/week (OR 0.71, 95% CI 0.49 to 1.03, p=0.07). Of the two transgender women who seroconverted during the OLE, both had drug levels below 350 fmol/punch in DBS, the level associated use of 2 tablets per week at the time of seroconversion. The lower concentrations were more likely if the transgender women used feminizing hormones.

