#### **9.6 Measures of Treatment Adherence**

Daily adherence will be directly observed by participants taking part in real time DOT video calls, or witnessed by study staff at the study visit if the drug is taken at the clinic. Study staff will monitor the FTC/TDF tablet be placed into the mouth, swallowed, and the mouth opened to verify the table is no longer present. Alternate documentations of pill taking as described in 9.4.1 may be used as back up measures if access to video capacity is impossible for participant. DOT will be recorded daily by the study team to document on the Drug Dispensation, Hormones and DOT log. Repeated failure to adhere to the DOT regimen will lead to discontinuation from study participation.

If participant fails to connect with study staff for the call, study staff will make every possible attempt to connect with participant. If participant misses the call and does not provide back up evidence of pill taking, it will be considered a missed dose.

If participant misses two or more study drug doses, the participant will be excluded from study participation.

DOT calls will capture hormone therapy adherence as well, which may be either directly observed if feasible, or verbal self-report. Hormone adherence will be captured on the Drug Dispensation, Hormones and DOT log.

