### **15.1 Data Sets Analyzed**

All eligible and dosed participants who are enrolled into the study and receive all doses of the study drug will be included in the pharmacokinetic analysis.

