### **15.3 Analysis of Primary Endpoint**

We will compare levels of TFV-DP in dried blood spots and rates of adverse events between trans men and trans women and a group of MSM historical controls from the iPrEx OLE study. We will compare log transformed TFV-DP levels using a linear mixed effects model with factors for group (trans men v. trans women v. MSM) and times (1, 2, 3 and 4 weeks after initiation) and their interaction with an unstructured covariance across visits and test for differences at between groups at each time point. If values appear to violate the normal distribution, we will obtain p-values and confidence intervals using the bootstrap. All p-values will be two-sided with p-value < 0.05 considered statistically significant. Adverse events will be compared using the Fisher exact test.

Adverse event rates will be coded by body system and MedDra classification term. Adverse events will be tabulated and will include the number of patients for whom the event occurred, the rate of occurrence, and the severity and relationship to study drug.

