### **15.4 Sample Size**

A sample size of 48 (24 trans women and 24 trans men) allows detection of a difference of 0.52 log difference (1.68 fold difference) in TFV-DP from dried blood spots with 81% power on a two-sided 0.05 level test at any time point between our trans participants and MSM historical controls. A difference of 0.70 log (2.0 fold difference) can be detected between either group (trans men or women) and MSM historical controls with 80% power on a two-sided 0.05 level test. This is sufficient to determine if the differences in drug

concentrations observed in iPrEx OLE between MSM and trans women were due to interactions with feminizing hormone drug-drug interactions.

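### The primary mixed model does not let the covariance differ by group, so standard errors may be too wide or too narrow if MSM controls vary more than observed trans participants

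*Combined protocol and SAP*

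**What the plan says.** Section 15.3 compares "log transformed TFV-DP levels using a linear mixed effects model with factors for group (trans men v. trans women v. MSM"), with weeks 1 to 4 as times and "their interaction with an unstructured covariance across visits and test for differences at between groups at each time point". The synopsis repeats the phrase "with an unstructured covariance across visits". Neither place says whether the matrix is common to the three groups or estimated by group. The one fallback reads: "If values appear to violate the normal distribution, we will obtain p-values and confidence intervals using the bootstrap". No resampling scheme is given.

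The groups differ in how they dose and how they are selected. Trans participants are on daily DOT (section 5.1). Section 9.6 states: "If participant misses two or more study drug doses, the participant will be excluded from study participation". Section 15.1 admits only those who "receive all doses of the study drug will be included in the pharmacokinetic analysis". Section 15.3 takes the controls from iPrEx OLE. On that study section 2.2 reports that "transgender participants had less time with protective drug concentrations (17% vs 35%, p<0.001"); the 35% is the MSM figure. Section 3 instead points to earlier MSM data in references 9-11, and reference 10 is, by its title, a directly observed dosing study.

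Section 15.4 says that 48 trans participants "allows detection of a difference of 0.52 log difference (1.68 fold difference") with 81% power against MSM, and gives 0.70 log with 80% power for one trans group of 24. It states neither an SD nor a number of controls. Section 15 defers detail to a later SAP, and no separate SAP is among the documents.

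**The concern.** "Unstructured" frees the variances and correlations across visits. It does not by itself free them across groups, and an analyst following section 15.3 would normally fit one matrix to everyone. The plan removes most adherence variation from two groups and, if the controls are ordinary iPrEx OLE participants, keeps it in the third. A shared matrix then averages two different variances and uses the average in every contrast.

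The consequence is clearest for trans men v. trans women. This is the one contrast in which both groups are directly observed, and MSM data enter it only through the shared variance. For contrasts with MSM, the confidence interval could be too wide, so that a modest hormone effect is missed, or too narrow, so that a chance difference is declared. The bootstrap does not settle this, because unequal variance does not trigger it.

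**Working it through.** **Step 1: the plan's own figures.** exp(0.52) = 1.68 and exp(0.70) = 2.01, so the logs are natural. The stated power cannot be reproduced directly, because SD and control number N are missing. Back-solving with one common SD:

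- 0.52/(1.960 + 0.878) = 0.1832 = SD × √(1/48 + 1/N)
- 0.70/(1.960 + 0.842) = 0.2499 = SD × √(1/24 + 1/N)
- Difference of squares: 0.06243 − 0.03358 = 0.02885 = SD² × (1/24 − 1/48), so SD² = 1.385 and SD = 1.18
- 1/N = 0.03358/1.385 − 1/48 = 0.00341, so N = 293

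This solution is not unique. Any N from about 150 up, with SD about 1.11 to 1.26, matches both statements within 2 points. So does one control per trans participant in each comparison (48 v. 48 and 24 v. 24) with SD 0.88, which gives 82.5% and 78.7%. Hence the two control scenarios below.

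**Step 2: assumptions.** SD under DOT: 0.3-0.5, with 0.7 as a check (assumed; the documents give none). MSM: SD 0.88 with 48 controls, or SD 1.18 with 293. The back-solve assumes a common SD; assigning that SD to MSM alone is a further assumption. A case with 24 controls (SD 0.88) is added to show direction. It is not a reading of section 15.4 as a whole: 48 v. 24 would have SE 0.88 × √(1/48 + 1/24) = 0.22 and about 66% power at 0.52.

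**Step 3: formulas, at one visit with complete data.** A shared matrix then reduces to the pooled variance at that visit:

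- s_p² = [46 s_T² + (N − 1) s_M²]/(45 + N)
- Shared SE = s_p √(1/n₁ + 1/n₂)
- Group-specific SE = √(s₁²/n₁ + s₂²/n₂)

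For trans men v. trans women the ratio of the two is s_p/s_T. Since s_p² is a weighted average of s_T² and s_M², this exceeds 1 at every N whenever s_M > s_T.

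Example, 48 controls and DOT SD 0.5: s_p = √[(46 × 0.25 + 47 × 0.7744)/93] = 0.718, and the ratio is 0.718/0.5 = 1.44.

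**Step 4: shared SE divided by group-specific SE.**

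| Controls (SD) | DOT SD | s_p | Trans men v. trans women | 24 v. MSM | 48 v. MSM |
|---|---|---|---|---|---|
| 24 (0.88) | 0.3 | 0.564 | 1.88 | 0.86 | 0.76 |
| 24 (0.88) | 0.5 | 0.652 | 1.30 | 0.91 | 0.84 |
| 48 (0.88) | 0.3 | 0.660 | 2.20 | 1.17 | 1.00 |
| 48 (0.88) | 0.5 | 0.718 | 1.44 | 1.10 | 1.00 |
| 293 (1.18) | 0.3 | 1.102 | 3.67 | 2.54 | 2.11 |
| 293 (1.18) | 0.5 | 1.112 | 2.22 | 1.92 | 1.74 |
| 293 (1.18) | 0.7 | 1.127 | 1.61 | 1.51 | 1.43 |

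With equal SDs every ratio is 1.00.

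**Step 5: error rate and power.** Two-sided type I error is about 2 × [1 − Φ(1.96 × ratio)]. With 24 controls, ratios of 0.91 to 0.76 give 7.4% to 13.5%. With 293 controls and DOT SD 0.3-0.5, the error for 24 v. MSM is below 0.02%.

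A simulation with MSM SD 1.18 and trans SD 0.59, one trans group v. MSM, agrees in direction. Type I error under pooling was 0.079, 0.029, 0.007 and 0.0006 with 24, 48, 100 and 300 controls. With group-specific variances (Welch) it was 0.048 to 0.053.

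Power with 293 controls:

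- Trans men v. trans women at an illustrative 0.50 log, DOT SD 0.3-0.5: 8-19% shared, 93% or more group-specific.
- 24 v. MSM at an illustrative 0.40 log, DOT SD 0.3-0.5: 26-31% shared, 90-99% group-specific.
- At the section 15.4 differences, DOT SD 0.3-0.7: shared power is still about 93-99% (0.70 log, 24 v. MSM) and 92-99% (0.52 log, 48 v. MSM).

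**The case against.** The strongest reply is that the plan never says the matrix is shared. That is true: sharing is inferred from usual practice, and a later SAP could specify otherwise. But section 15.3 makes no provision for separate matrices, so the point stands as something to write in.

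A reader might go further and infer that every between-group standard error is wrong, or that the tests are bound to be far too conservative. The documents do not support that. With equal SDs there is no error; 48 v. 48 comes out right even with unequal SDs; few controls make the tests liberal. A ratio of about 12 controls per trans group is one solution of section 15.4 among many. A real effect would not necessarily be missed either, because power at the design differences stays above 90% even in the case with 293 controls.

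Nor is unequal variance established. The SD under DOT is assumed. Sections 9.4.3 and 10.4 accept audio calls, self-filmed video or a text message as back-up, so observation is not complete. The 35% describes OLE MSM in general, not the undefined subset to be used at weeks 1-4. Section 3 cites sources that include a directly observed study. If the controls come from there, much of the expected difference in spread may disappear.

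Trans men v. trans women is outside the objective in section 4.1 and is not powered in section 15.4. It is, however, among the group tests that section 15.3 calls for.

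Finally, mixed adherence could itself produce non-normal values and trigger the bootstrap, and resampling within group would handle unequal variance. With no scheme stated, the fallback can be counted neither as a remedy nor as a failure.

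**Conclusion.** The point holds in a limited form. The plan does not let the covariance differ by group, although its own design makes a larger MSM variance likely. If MSM are more variable, the trans men v. trans women SE is too wide whatever the number of controls: about 1.4-2.2 times with 48 controls (SD 0.88) and 2.2-3.7 times with about 290 (SD 1.18). Against MSM the direction depends on the control number: about 1.9-2.5 times too wide for 24 v. about 290, about right for 48 v. 48, and about 0.76-0.91 of its proper size with 24 controls, which puts type I error above 5%.

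These sizes rest on an assumed DOT SD of 0.3-0.5 and on control numbers and SDs that the documents do not state. The lack of provision for separate covariances is firm. The size of the error is conditional.

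**What to change.** In section 15.3 and the synopsis, state that the covariance is estimated separately by group, with at least one unstructured matrix for the two DOT groups and another for MSM, and use Kenward-Roger or Satterthwaite degrees of freedom. State that any bootstrap resamples whole participants within group.

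In section 15.4, give the number and source of the controls, reconciling section 3 with section 15.3. Give separate SDs for DOT participants and controls, and recompute the detectable differences from them.

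The cost is small. A matrix over four visits has 4 × 5/2 = 10 parameters, so the two-matrix version adds 10 and loses a few degrees of freedom. No new participants or measurements are needed, and little is lost if the variances prove equal. The change repairs the standard errors only. If the controls dosed unobserved, the difference in means still mixes adherence with any hormone effect, and that needs its own remedy.

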TEST PRODUCT, DOSE, AND ROUTE OF ADMINISTRATION	FDA approved Truvada (one tablet containing 200 mg of emtricitabine or FTC and 300 mg of tenofovir disoproxil fumarate or TDF) once daily taken orally with or without food. Gilead Sciences will dispense medication to through their FDA approved commercial packaging of 30 tablets per bottle with an included desiccant.
CONTROL PRODUCT, DOSE AND ROUTE OF ADMINISTRATION	N/A
DURATION OF PARTICIPANT PARTICIPATION AND DURATION OF STUDY	
Participants will be on study for up to 56 days
 
Screening: up to 28 days
 
Treatment: 4 weeks or 28 days (participants come to clinic weekly and DOT via video calls)
 
Follow-up: n/a
 
The total duration of the study is expected to be 7-9 months: 1-3 months for participant recruitment and 6 for final participant follow-up.

CONCOMITANT MEDICATIONS	
Allowed:
 
Testosterone, estradiol, spironolactone,
 
Prohibited:
 
ART, including nucleoside analogs, non-nucleoside reverse transcriptase inhibitors, protease inhibitors or investigational antiretroviral agents, interferon (alpha, beta, or gamma) or interleukin (e.g., IL-2) therapy, aminoglycoside antibiotics, amphotericin B, cidofovir, systemic chemotherapeutic agents, other agents with significant nephrotoxic potential, other agents that may inhibit or compete for elimination via active renal tubular secretion (e.g., probenecid), and/or other investigational agents

EFFICACY EVALUATIONS	N/A
PRIMARY ENDPOINT	Concentrations of FTC triphosphate and tenofovir diphosphate (TFV-DP) in Dried Blood Spots (DBS)
SECONDARY ENDPOINTS	N/A
OTHER EVALUATIONS	N/A

SAFETY EVALUATIONS	Incidence of adverse events ( AEs will be collected as part of the weekly visit if participants report AEs )
PLANNED INTERIM ANALYSES	N/A

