### **4.2 Secondary Objectives**

To determine if daily oral FTC/TDF is associated with comparable rates of adverse events (AEs) in transgender women and in transgender men compared to historical controls in non-transgender MSM.

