### 6.3 Safety Evaluations

AEs: Grade 1 and above as reported side effects on a structured instrument

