### **12.4 Replacement of Participants**

Participants who withdraw from the study treatment may be replaced.

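### A Fisher test of difference cannot show that adverse event rates are comparable, and the protocol gives no interval, margin or control time window for that objective

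*Combined protocol and SAP*

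**What the plan says.** Section 4.2 states the secondary objective: "To determine if daily oral FTC/TDF is associated with comparable rates of adverse events (AEs) in transgender women and in transgender men", relative to historical non-transgender MSM. The word *comparable* is not defined, and section 6.2 lists no secondary endpoints.

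Section 15.3 and the synopsis give one inferential method: "Adverse events will be compared using the Fisher exact test". The general rule there is "All p-values will be two-sided with p-value < 0.05 considered statistically significant". Section 15.3 also plans descriptive tables by body system and MedDRA term, with severity and relationship to study drug.

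Section 15.4 sizes the study on TFV-DP alone. It gives no control AE rate, no number of controls, and no AE power or margin.

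The controls come from iPrEx OLE. Weeks 1 to 4 are named as time points for the TFV-DP model, but no window is stated for control AEs. Trans participants take study drug for 28 to 30 days (section 5.1).

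The only analysis set, in section 15.1, is for drug levels: those who "receive all doses of the study drug will be included in the pharmacokinetic analysis". No set is named for AEs, and "Participants who withdraw from the study treatment may be replaced" (section 12.4).

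**The concern.** The objective and the method do not match. Fisher's test asks whether the data contradict equal proportions. A claim that rates are comparable needs the opposite: evidence that an excess large enough to matter has been ruled out. A non-significant p-value does not supply that, least of all with 24 people in a group. The protocol offers nothing else on which a statement of comparability could rest.

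Two gaps add to this. A Fisher test on the proportion of participants with an event takes no account of time at risk. If control AEs were counted over more than about 4 weeks, the control proportion would be higher for that reason alone and the trans groups would look safer than they are. And with withdrawal and replacement allowed, the AE denominator has to be stated.

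At stake is the trial's only safety comparison, in two populations for which the protocol says PrEP data are sparse or absent.

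**Working it through.** **Inputs from the protocol.** 24 trans women and 24 trans men (15.4); two-sided 0.05 and Fisher's test (15.3); AEs of Grade 1 and above (6.3).

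**Inputs not given, so assumed.** Control AE proportion p: 10% to 40%. Number of controls M: 24 to 1,000.

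**The plan's own figures.** There is no AE power to reproduce. The TFV-DP power in 15.4 cannot be reproduced either, because the SD and M are missing. Its two statements can only be checked against each other, using

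SD = δ / [(1.960 + z_power) × √(1/n + 1/M)]

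- All 48, δ = 0.52, 81% power, M = 292: 0.52 / (2.838 × √(1/48 + 1/292)) = 0.52 / (2.838 × 0.1557) = 1.18.
- One group of 24, δ = 0.70, 80% power, M = 292: 0.70 / (2.802 × √(1/24 + 1/292)) = 0.70 / (2.802 × 0.2123) = 1.18.

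The statements therefore agree at about 292 controls. They do not pin M down: the two implied SDs are 1.14 and 1.16 at M = 200, and 1.24 and 1.21 at M = 1,000. Nor need the AE control set be the same as the TFV-DP control set. I use 292 as a working assumption and vary it.

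**Power of Fisher's test against a true doubling.** Exact enumeration, with x₁ events among n trans participants and x₂ among M controls:

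Power = Σ Bin(x₁; n, 2p) × Bin(x₂; M, p), summed over all (x₁, x₂) with two-sided Fisher p < 0.05.

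| Control → trans | 24 v. 24 | 24 v. 292 | 24 v. 1,000 | 48 (pooled) v. 292 |
|---|---|---|---|---|
| 10% → 20% | 10% | 31% | 34% | 46% |
| 20% → 40% | 24% | 56% | 59% | 81% |
| 30% → 60% | 47% | 82% | 85% | 97% |
| 40% → 80% | 76% | 97% | 98% | >99% |

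With 292 controls, a doubling in one trans group gives a non-significant result 69% of the time at a 10% control rate and 44% at 20%. Going to 1,000 controls adds about 3 points at each of these rates, because the group of 24 is the limiting factor.

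**What an interval could show.** Assume equal true proportions p and 300 controls, so that 1/24 + 1/300 = 0.045. The approximate 95% half-width is 1.96 × √(p(1−p) × 0.045), and the chance that the upper limit excludes a doubling is Φ(p / √(p(1−p) × 0.045) − 1.96).

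| p | Half-width (points) | Chance of excluding a doubling |
|---|---|---|
| 10% | 12.5 | 35% |
| 20% | 16.6 | 65% |
| 30% | 19.1 | 87% |
| 40% | 20.4 | 97% |

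A doubling is used here only as a yardstick; the protocol defines no margin.

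**Time window.** Trans participants contribute 28 to 30 days. Control follow-up for AEs is not stated, so the bias cannot be sized. A constant-hazard projection would not be safe, since section 3.1 says side effects may arise in the first weeks and usually resolve.

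**The case against.** The protocol never says that a p-value of 0.05 or more will be read as comparable. A reader might infer that rule because no other criterion is given, but it is not written. Section 15.3 also plans descriptive AE tables, and the opening of section 15 promises a detailed SAP. This stands as a limit on what can be claimed: the fault is a missing criterion, not a stated wrong one. The promise of a later SAP does not supply the criterion in the current text.

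Power may also be adequate. Any AE of Grade 1 or above could be common, and at control rates of 30% to 40% a doubling would be detected 82% to 97% of the time with 292 controls. Pooling all 48 gives 81% at a 20% control rate. This also stands, with two limits. The objective names each trans group, and the protocol does not say whether AEs are tested per group, pooled or in one three-group table. And 15.3 codes events by body system and MedDRA term, where low rates are to be expected.

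Two stronger readings are not supported:

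- *That AEs are analysed only in people who took every dose.* The restriction in 15.1 is expressly for the pharmacokinetic analysis. AEs are captured throughout the study (10.1.8) and recorded with questionnaires at the early withdrawal visit (11.6). What is missing is a named AE set.
- *That AE capture is left open between solicited and volunteered reports.* The synopsis has "AEs will be collected as part of the weekly visit if participants report AEs", but 6.3 has "AEs: Grade 1 and above as reported side effects on a structured instrument", and sections 10.1.8, 11.4 to 11.6 and 12.1 consistently provide for questionnaires.

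**Conclusion.** The point holds as a mismatch between objective and method. A comparability objective has only a difference test, with no interval, margin or other criterion. Assuming 292 controls, the test of one trans group would miss a true doubling 69% of the time at a 10% control rate and 44% at 20%, but only 18% at 30% and 3% at 40%. With 24 controls the misses at 10% and 20% would be 90% and 76%. These sizes rest on assumed control rates and control numbers. The problem is sharpest for less common events, such as individual MedDRA terms.

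The unstated control AE window and the unnamed AE analysis set are real omissions. The first would bias a comparison of proportions if control AEs were counted for longer than the trial's 4 weeks; the size is unknown. Because the objective is secondary and the remedy is cheap, this should be corrected before the SAP is fixed, but it does not touch the primary drug-level comparison.

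**What to change.** In section 15.3, and carried into the SAP:

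1. For each trans group against MSM, report the difference in the proportion of participants with at least one AE and its 95% interval by one named method, for example Newcombe. Naming one matters because methods can disagree near the boundary: 9/24 against 58/292 (illustrative counts) gives Fisher p = 0.065 but a Newcombe interval of +0.6 to +37.9 points.
2. State that p ≥ 0.05 is not evidence of comparability. Base any such statement on whether the upper limit excludes a difference that the investigators prespecify and justify.
3. Count AEs in both sources over the first 4 weeks after first dose, with the same grade threshold and symptom list.
4. Define the AE set as every participant who took at least one dose, including those later withdrawn or replaced.

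The cost is SAP wording and a date and symptom filter on the control data; no extra participants or visits are needed. The drawback is width. With 24 per group and an assumed 300 controls, intervals would run about ±12.5 to ±20.4 points for control rates of 10% to 40%, so any claim of comparability will be weaker. If the controls' AE data cannot be matched on window, grade or symptom list, the comparison should be reported as descriptive.
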